## 5.6 Multiplicity

- Given the exploratory nature of this project and the inclusion of multiple outcomes, formal adjustment for multiplicity (e.g., Bonferroni or Holm corrections) will not be applied. Instead, the following principles will guide interpretation:
  - Primary vs. Secondary Outcomes: If designated, primary outcomes will be the main focus of interpretation. Secondary outcomes and subgroup analyses will be considered hypothesis-generating.
  - Subgroup and Sensitivity Analyses: Comparisons across subgroups (e.g., completers versus non-completers, site-level differences) will be viewed as exploratory and interpreted cautiously.
  - Interpretation Strategy: Results will be evaluated in terms of effect sizes, 95% confidence intervals, and the consistency of findings across related measures, with attention to clinical and practical significance.
  - Transparency: All pre-specified outcomes will be reported regardless of statistical significance to minimize selective outcome reporting.

## 5.7 Subgroup Analyses

- Baseline Comparisons Between Groups
  - To assess whether participants who completed the study protocol differ from those who did not at baseline, independent samples t-tests will be conducted for all continuous baseline outcome variables (e.g., MMSE, agitation, quality of life, depression, loneliness, satisfaction with care).
  - Assumptions: Levene's Test for Equality of Variances will be used to assess homogeneity of variance. If assumptions are violated, the t-test results under "equal variances not assumed" will be reported.
  - Effect Sizes: Cohen's d will be calculated to estimate the standardized mean difference between groups. Effect sizes will be interpreted as small (~0.20), medium (~0.50), and large (~0.80).
  - $\circ$  Significance Threshold: All tests will use two-tailed significance testing with  $\alpha = .05$ .

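### Section 5.7's Levene-gated t-test does not quite hold 5% when variances differ, and separately its .05 threshold has too little power for non-significance to show that loss was unselective

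*Combined protocol and SAP*

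**What the plan says.** SAP section 5.7 sets out a baseline comparison whose purpose is "To assess whether participants who completed the study protocol differ from those who did not at baseline". The method is that "independent samples t-tests will be conducted for all continuous baseline outcome variables", with MMSE, agitation, quality of life, depression, loneliness and satisfaction with care as examples.

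- **Choice of test:** "Levene's Test for Equality of Variances will be used to assess homogeneity of variance". The switch rule begins "If assumptions are violated, the t-test results under" and names the unequal-variance row as the one then reported. Otherwise the pooled result stands.
- **Threshold:** "All tests will use two-tailed significance testing with" an alpha of .05.
- **Effect size:** "Cohen's d will be calculated to estimate the standardized mean difference between groups", read against conventional values of 0.20, 0.50 and 0.80.

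Section 5.6 covers subgroup and sensitivity comparisons and names this one: "e.g., completers versus non-completers, site-level differences) will be viewed as exploratory and interpreted cautiously". It also says that results are to be judged on effect sizes, 95% confidence intervals and consistency. Sections 5.1.7 and 8.3 require confidence intervals generally. No section gives the number of non-completers, the power of this check, or an action that depends on its result.

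**The concern.** There are two separate issues.

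First, completers will probably outnumber non-completers by a wide margin. That is the setting in which the pooled t-test is most sensitive to unequal variances. A preliminary Levene test guards against this only when it rejects, and with few non-completers it often will not. The reported test then does not have its nominal error rate.

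Second, a small non-completer group gives a .05 test little power. The ITT set in section 3.4 needs at least one post-intervention measure, and section 5.2 rules out multiple imputation and likelihood methods. Residents with no follow-up therefore leave the pre-post analyses, and this comparison is the main inferential look at whether they differed at baseline. If a non-significant result is taken as reassurance, it carries more weight than it can bear.

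**Working it through.** **The plan's own figure.** Section 3.1 states 80% power at d = 0.35-0.40, two-sided .05, for the paired primary tests. By n = ((1.960 + 0.842)/d)², that needs 65 or 50 pairs (67 or 52 with the exact t). Allowing for 20-25% attrition, this is 52/0.80 = 65 to 67/0.75 = 90 enrolled. The 160 planned therefore exceeds the stated target but is not derived from it. No power is stated for the completer check, so there is no figure to reproduce there.

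**Group sizes (assumed).**
- 128 v 32 and 120 v 40: SAP section 3.1's 160 residents with 20% and 25% attrition.
- 107 v 53: 160 planned less the 107 analysed (section 3.2).
- 107 v 135: the protocol's 242 residents (Specific Aim 3) less 107.
- 218 v 24: 242 with the protocol's attrition of about 10%.

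The SAP and protocol disagree on both planned number and attrition, and the two should be reconciled.

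**Why the pooled test drifts.** Take 128 v 32 with a non-completer SD of 1.25.
- Pooled variance = (127 × 1 + 31 × 1.5625)/158 = 1.110, so the pooled test uses SE² = 1.110 × (1/128 + 1/32) = 0.0434.
- The true SE² = 1/128 + 1.5625/32 = 0.0566.
- The pooled SE is √(0.0434/0.0566) = 0.875 of the true one. The real critical value is about 1.96 × 0.875 = 1.72, an error of about 8.6%.

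With an SD of 0.8 the same steps give a ratio of about 1.14 and an error of about 2.5%. Levene's test corrects only part of this.

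**Simulated type I error** (normal scores, Levene at .05, 40,000 runs per row, Monte Carlo SE about 0.1 point):

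| Groups | Non-completer SD ratio | Levene rejects | Pooled | SAP rule | Welch |
|---|---|---|---|---|---|
| 128 v 32 | 1.25 | 33% | 8.6% | 6.9% | 5.0% |
| 120 v 40 | 1.25 | 37% | 8.0% | 6.5% | 5.1% |
| 107 v 53 | 1.25 | 42% | 6.8% | 5.7% | 4.9% |
| 128 v 32 | 0.8 | 28% | 2.5% | 3.8% | 4.9% |
| 120 v 40 | 0.8 | 33% | 2.8% | 3.9% | 4.9% |
| 107 v 53 | 0.8 | 40% | 3.4% | 4.4% | 5.0% |

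Taken with shorter repeat runs, the SAP rule lies at 5.7-7.1% and 3.7-4.7%. With equal SDs it gives 4.9-5.1%. At an SD ratio of 2 Levene almost always rejects and the rate returns to 5.0-5.2%.

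**Power.** The noncentrality is d/√(1/n₁ + 1/n₂) with n₁ + n₂ − 2 degrees of freedom. The 95% half-width for d near zero is 1.96 × √(1/n₁ + 1/n₂).

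| Groups | √(1/n₁ + 1/n₂) | Noncentrality at d = 0.35 | Power | Half-width |
|---|---|---|---|---|
| 128 v 32 | 0.198 | 1.77 | 42% | 0.39 |
| 120 v 40 | 0.183 | 1.92 | 48% | 0.36 |
| 107 v 53 | 0.168 | 2.08 | 54% | 0.33 |
| 107 v 135 | 0.129 | 2.70 | 77% | 0.25 |

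At 218 v 24 power is 37%.

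**Does Levene cost power?** With equal variances and d = 0.35, simulated power under the SAP rule against Welch alone is 42% v 41%, 48% v 48% and 55% v 54% for the three SAP-based splits. It does not.

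**The case against.** The strongest reply is that nothing in the plan is decided by this p-value. Section 5.7 itself requires Cohen's d. Section 5.6 makes the comparison exploratory and judges it on effect sizes and intervals, and no action follows from the result. That stands. A reader might infer from the .05 threshold that the plan will declare loss unselective when p exceeds .05, but the documents do not say so. What remains is that 5.7 restates a threshold without 5.6's reading rule and does not warn against that inference.

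A reader might also infer that the Levene step is why the check would miss a difference. The calculation rules this out: the low power comes from the small non-completer group, and Welch does not cure it.

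Other replies also have force:
- The value d = 0.35 is borrowed from the paired-change power statement. The documents do not set it as a relevant baseline difference.
- The SD ratio of 1.25 is assumed and lies near where the drift is largest.
- The shift in the analysed mean is modest. At d = 0.35 it is 0.35 × 53/160 = 0.12 SD for 107 v 53, and 0.35 × 32/160 = 0.07 SD for 128 v 32.
- The primary analysis is within-person change, so a baseline shift bears on generalisability rather than directly biasing the paired difference.
- Section 8.2 also plans a flow diagram and, where applicable, outcomes stratified by completion, so this is not the only planned look at loss.

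**Conclusion.** The point holds as a minor one, in two independent parts.

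1. At SAP-based group sizes the Levene-gated rule departs from 5% by roughly one to two points in either direction when SDs differ moderately. Always using Welch removes this for essentially no loss of power. The sizes rest on normal scores, Levene at .05 and assumed SD ratios of 1.25 and 0.8.

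2. The .05 test would miss a baseline difference of d = 0.35 in about 46-58% of cases at those sizes, so non-significance is weak evidence that loss was unselective. This depends on a non-completer count that the documents do not give. If 242 were enrolled and 107 completed, power would be 77% and the point much weaker.

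Neither part changes a primary result. The documents do not support a reading that the plan decides selectivity by p-value, or that the pre-test makes the check insensitive.

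**What to change.** In SAP section 5.7:

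1. Delete the Levene step and always report the unequal-variance (Welch) row, which SPSS prints anyway.
2. Carry section 5.6's interpretation rule into 5.7: read the standardised difference with its 95% CI (half-width about 0.33-0.39 at SAP-based sizes) rather than against the .05 threshold.
3. Add a sentence that a non-significant difference does not show that loss was unselective.
4. State the number of completers and non-completers beside the results.

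Do not add a rule that flags |d| of 0.20 or more. With no selective loss at all it would fire in about 24-31% of comparisons per variable at SAP-based sizes, because 0.20 is only 1.0 to 1.2 standard errors (0.20/0.198 to 0.20/0.168).

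The cost is a few lines of SAP wording. No new data or analyses are needed, and the loss of power if variances are truly equal is about one percentage point or less.

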## 6. Data Management

All study data will be managed to ensure accuracy, integrity, and confidentiality, in compliance with institutional policies, NIH/NIA guidelines, and Good Clinical Data Management Practices (GCDMP).

[All study data will be captured in a secure electronic format at the Benjamin Rose Institute. To ensure accuracy, double-entry verification will be performed, and any data queries will be documented and resolved prior to analysis. Before analysis begins, all datasets will be deidentified to protect participant confidentiality.]

#### 6.1 Data Capture

- Data will be collected in a secure electronic format using the Benjamin Rose Institute on Aging's approved data systems, with access restricted to authorized study personnel only.
- Where paper case report forms (CRFs) or checklists are used in the field, data will be entered electronically by trained study staff within 5 business days of collection.

## 6.2 Data Entry and Verification

- A double-entry process will be used for quantitative data to minimize transcription errors.
- Automated range checks and logic checks (e.g., impossible dates, out-of-range scores) will be built into the data entry system to prevent invalid entries.
- Data queries will be generated automatically or manually by the data management team and documented in a query log. Queries will be reviewed and resolved by the study coordinator or PI prior to database lock.

## 6.3 Data Cleaning and Quality Control

- Regular data quality checks will be conducted (e.g., completeness, consistency across timepoints, adherence to allowable ranges).
- Any modifications to the dataset (e.g., corrections, imputations) and collected surveys will be documented with date, rationale, and responsible staff initials to maintain a full audit trail.
- Interim datasets may be produced for monitoring, but final analyses will only be performed after database lock.

## 6.4 Confidentiality and De-Identification

- All datasets used for analysis will be de-identified by removing direct identifiers and replacing participant IDs with unique study codes.
- A master linking file will be stored separately on a secure, access-restricted server and accessible only to the PI and designated data manager.
- All electronic data will be stored on encrypted, password-protected servers that comply with institutional IT security standards.

#### 6.5 Data Retention and Archiving

• Study data will be retained for at least 7 years after completion of the study, consistent with institutional policy and NIH requirements.

- At study closeout, data will be archived in a secure format, with clear documentation of file structures, variable definitions, and metadata to support future re-use if permitted.
- If applicable, de-identified datasets may be shared with NIH data repositories (e.g., NIA-approved archives) following sponsor and IRB approval.

## 6.6 Data Access and Oversight

- Access to the data will be role-based, with permissions granted according to study responsibilities.
- A data manager will oversee ongoing data integrity, maintain audit trails, and ensure compliance with this SAP.
- Any breaches or irregularities will be reported to the PI and IRB per institutional policy.

## 7. Quality Control

Quality control procedures will be applied throughout the study to ensure accuracy, reliability, and adherence to protocol.

- Training and Standardization: All staff involved in data collection and entry will receive standardized training, with refresher training provided as needed.
- Ongoing Monitoring: The data manager will conduct routine checks for completeness, timeliness, and consistency. Discrepancies will be logged, investigated, and resolved in collaboration with the PI.
- Audit Trail: All data modifications will be documented with date, rationale, and staff initials.
- Pre-analysis Review: Prior to database lock, a final quality review will be conducted, including verification of key variables against source documents, reconciliation of missing data, and confirmation of resolution of all outstanding queries.
- Documentation: A QC log will be maintained to document all procedures performed, issues identified, and corrective actions taken.

These measures ensure that all analyses conducted under this SAP are based on high-quality, reliable data.

## 8. Reporting

- Results reported according to CONSORT extension for non-randomized trial
- Tables/Figures will include:
  - Participant flow (CONSORT diagram)
  - Baseline characteristics (by staff/resident)
  - Pre-post outcome tables (means, SDs, p-values, effect sizes)
  - Subgroup analyses where applicable.

## 8.1 Reporting Standards

 Results will be reported in accordance with the CONSORT 2017 extension for nonrandomized trials and best practices for transparent reporting of clinical and implementation studies. Reporting will also comply with ClinicalTrials.gov requirements, including timely submission of summary-level results within 12 months of study completion.

## 8.2 Planned Tables, Figures, and Listings (TFLs)

The following tables and figures will be included in study reports and publications:

- Participant Flow: A CONSORT-style diagram summarizing enrollment, exclusions, intervention completion, and analysis populations (staff and residents).
- Baseline Characteristics: Tables summarizing demographics, cognitive/functional characteristics, and relevant staff/resident attributes by study group.
- Pre-Post Outcomes: Summary tables of primary and secondary outcomes, reporting means, standard deviations, sample sizes, p-values, and effect sizes (Cohen's d).
- Subgroup Analyses: Where applicable, outcomes stratified by relevant subgroups (e.g., completers of the intervention versus non-completers).
- Supplementary Figures: Graphical displays of key outcomes over time (e.g., line graphs, bar charts).

#### 8.3 Statistical Summaries

- Continuous variables will be reported using means and standard deviations (or medians and interquartile ranges, as appropriate).
- Categorical variables will be reported as counts and percentages.
- All hypothesis tests will be reported with p-values and 95% confidence intervals.
- Effect sizes will be presented for primary and secondary outcomes.
- Missing data will be summarized by frequency and percentage.

### 8.4 ClinicalTrials.gov Reporting

- Results will be uploaded to ClinicalTrials.gov following registry requirements.
- Only summary-level data will be reported (no individual-level data).
- Pre-specified outcomes from the protocol and SAP will be included to ensure consistency and transparency.
- Adherence to reporting timelines will be maintained in compliance with NIH/NIA expectations.

## 8.5 Transparency and Deviations

 Any deviations from the pre-specified analysis plan will be documented, justified, and reported in both the ClinicalTrials.gov results submission and any manuscripts.

- Protocol deviations (e.g., exclusion due to missing >50% of composite variables) will be summarized in tabular form.
- Harms/adverse events (if applicable) will be reported descriptively.

#### 8.6 Dissemination

- Findings will be disseminated in peer-reviewed publications, presentations at national conferences, and summary reports for participating sites and stakeholders.
- Supplementary materials (e.g., detailed statistical outputs, additional tables/figures) may be provided in online appendices.
- No individual participant data (IPD) will be shared outside the study team unless required by the sponsor or IRB.
